8.8 Analysis of Roll-in Subjects

Roll-in subjects will be summarized using descriptive statistics. No formal hypothesis testing will be done on this group.

Time to ambulation will summarized using the mean, median, standard deviation, sample size, minimum, and maximum. A 95% confidence interval for the average time to hemostasis will be calculated using the T-distribution.

Time to hemostasis will first be summarized across access sites within each subject by calculating the mean time to hemostasis by averaging the individual site-specific times. Time to hemostasis will then be summarized across subjects by calculating the mean, median, standard deviation, sample size, minimum, and maximum. A 95% confidence interval for the average time to hemostasis will be calculated using the T-distribution.

The proportion of roll-in subjects experiencing a major access related complication will be calculated along with a 95% confidence interval constructed using the Clopper-Pearson method.

8.9 Protocol Deviations

Protocol deviations will be listed by category. Descriptive statistics will be used to summarize the number of times a deviation happened over the course of the trial.

9 STUDY SITE POOLABILITY

Study site poolability for the primary endpoint of time to ambulation will be analyzed using a two-way analysis of variance (ANOVA) model. The first factor in this model will be treatment group and the second factor will be study site. The treatment group by study site interaction will also be added to the model. If the interaction term is not significant at the 0.15 level, then the study sites will be pooled for the analysis of this endpoint.

Study site poolability for the primary endpoint of time to hemostasis will be analyzed using the general linear mixed model outlined in section 5. To that model fixed effects for study site and treatment group by study site interaction will be added. If the interaction term is not significant at the 0.15 level, then the study sites will be pooled for the analysis of this endpoint.

Study site poolability for the safety endpoint will be analyzed on a per limb basis. A logistic regression model with main effects of treatment group and study site along with an interaction term between those main effects will be fit to the data. If the interaction term is not significant at the 0.15 level, then the study sites will be pooled for the analysis of this endpoint.

10 INTERIM ANALYSIS

An interim analysis in support of a CE Mark submission will be conducted to analyze initial subjects randomized to the treatment arm only with respect to efficacy and safety. This interim analysis is not intended to support a decision to continue or to discontinue the trial, or to implement any modifications to trial procedures. To alleviate potential statistical and operational bias that may be introduced, the execution of the interim analysis shall be a completely confidential process to the study team. All sponsor staff, staff contracted by the sponsor, and investigator staff directly involved in the conduct of the ongoing IDE trial will remain blind to the process and results of the analyses, with the exception of contracted resources involved in the execution of the interim analysis and submission of the results on behalf of the sponsor. Endpoints to be evaluated using descriptive statistics are as follows:

- Primary efficacy: Time to Ambulation and Time to Hemostasis
- Secondary efficacy:
- Time to Discharge Eligibility, Procedure success, and Device Success
- Primary safety: rate of major complications related to the access site.
- Secondary safety: rate of minor complications related to the access site.

This is a single-arm analysis, therefore subjects randomized to control arm will be excluded from the interim analysis. A sample size of 68 sequential subjects randomized to treatment arm will be collected for the interim analysis. A final clinical report will be prepared at the conclusion of the interim analysis by an agent of the sponsor who is

independent from the conduct of the study. The report will be unblinded following the collection of the last patient's procedure data.

11 HANDLING OF MISSING DATA

While all reasonable efforts will be made to obtain the data required to evaluate this endpoint, it is expected that some subjects may not be able to provide data due to several reasons (loss to follow-up, study withdrawal, death). For all primary and secondary analyses, no imputation of missing data is planned. Subjects who have ascertainment of status at a later out-of-window date (for example, subjects who are known to be free of events past discharge but missed the discharge visit) are not considered missing as their status is known and their data will be used as noted previously. The primary endpoint rate will be calculated as the number of subjects who had an event prior to the milestone visit divided by the number of evaluable subjects who had sufficient follow up (e.g., at least discharge visit) plus any subjects who had an event prior to the milestone visit.

A sensitivity analysis will be conducted for the endpoints of time to hemostasis, time to ambulation, and time to discharge eligibility using a simple pattern mixture model approach. For each treatment group, the overall mean is a weighted average of the observed data and the unobserved data. Assumptions on the unobserved data need to be used in order to assess the sensitivity of the study conclusions. For the control group, the mean of the unobserved data will be set equal to that of the observed data essentially assuming the missing data are missing at random. For the MYNX CONTROLTM Venous VCD group, the mean of the unobserved data will be incrementally increased by a pre-specified Δ until the overall interpretation of the endpoint changes. For time to hemostasis, the mean of the unobserved data will be increased in increments of 1 minute. For time to ambulation and time to discharge eligibility, Δ will be increased in increments of 0.5 hour. Once Δ has increased to the point that the endpoint conclusions change, then the feasibility of that increase will be assessed from a clinical standpoint.

The same type of sensitivity analysis will be done for the safety endpoint where the unobserved data in both groups starts out the same as the observed data. The sensitivity analysis for safety will be performed using the logit of the observed proportion of limbs with a major complication. The logit in the MYNX CONTROL[™] Venous VCD group will then be incrementally increased until non-inferiority between the two groups cannot be established. This change in logit will then be interpreted from a clinical standpoint.

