14.5 Lost to Follow-up

For all active subjects, the site must first make three (3) contact attempts to reach the subject. If unsuccessful, the Investigator must then send a certified letter to the subject. All contact attempts must be adequately documented in the subject's source documents. When possible, the subject's primary care physician should also be asked for assistance with contacting the subject.

The subject will be considered lost to-follow-up only under the following circumstances:

- The site learns that all methods of contacting the subject are no longer viable (e.g., telephone number not in service, no forwarding address provided, no current/correct contact information available from the subject's primary care physician).
- Failure to reach/hear from the subject for the final protocol-required follow-up visit after all required contact attempts have been made.

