16.9.1 Primary Analysis

Efficacy

The primary efficacy endpoints will be analyzed separately.

The average time to ambulation in each treatment group will be compared using a standard T-test.

The average time to hemostasis will be compared to the treatment groups using a generalized linear mixed model where subject is considered a random effect with multiple access sites. The times to hemostasis in the manual compression group will be reduced by 5 minutes to account for the hypothesis that the time to hemostasis for the MYNX CONTROL[™] Venous VCD is at least 5 minutes less than manual compression. The analysis will consist of testing the coefficient on the fixed effect for treatment group. If that coefficient is found to be significantly different from zero, then the direction will be evaluated to assure that the hemostasis time is reduced on average when using MYNX CONTROL [™] Venous VCD.

Safety

The safety analysis will be completed on a per-limb basis.

This endpoint will be analyzed using a GEE approach for a logistic regression model with a compound symmetric working covariance structure where occurrence of an AE is the binary response variable and treatment group is the only explanatory variable. Least square means for each treatment group and the risk difference between groups will be calculated along with the two-sided 95% confidence interval. The one-sided 97.5% confidence bound (equivalent to the appropriate bound from the two-sided 95% interval) will be compared to the non-inferiority window. If the upper bound is less than the non-inferiority window, then the two treatment groups will be considered non-inferior relative to the proportion of limbs experiencing a major venous access site closure-related complication.

As a supplementary analysis, a generalized linear mixed model will be used where subject will be entered into the model as a random effect and a compound symmetric correlation structure applied to those subjects contributing two limbs.

Version: 3.0 / 31Jan2023

Trial Success

This trial will be considered a success if both primary efficacy endpoints and the primary safety endpoint are achieved.

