16.11 Missing Data

While all reasonable efforts will be made to obtain the data required to evaluate this endpoint, it is expected that some patients may not be able to provide data due to several reasons (loss to follow-up, study withdrawal, death). For all primary and secondary analyses, no imputation of missing data is planned. Patients who have ascertainment of status at a later out-of-window date (for example, patients who are known to be free of events past discharge eligibility but missed the discharge visit) are not considered missing as their status is known and their data will be used as noted previously. The primary endpoint rate will be calculated as the number of patients who had an event prior to the milestone visit divided by the number of evaluable patients who had sufficient follow up (e.g., at least discharge visit) plus any patients who had an event prior to the milestone visit. In other words, the denominator will be adjusted for missing follow up data.

A sensitivity analysis will be done to assess the impact of missing data on the conclusion of the primary analyses. Details of the analysis are provided in the SAP.

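### The missing-data rule offers the discharge visit as its only example of sufficient follow-up for a primary safety rate that runs through 30 days, and leaves the milestone visit undefined

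*SAP*

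**What the plan says.** - **Endpoint.** Protocol 11.1.1 and SAP 4.1 run the primary safety rate through 30 days post procedure. It is the only primary endpoint that is a rate. One component is nerve injury still present at 30-day follow-up.
- **Denominator.** SAP 11 takes subjects with an event before the milestone visit, "divided by the number of evaluable subjects who had sufficient follow up (e.g., at least discharge visit"), plus any subject with an earlier event. Protocol 16.11 has the same rule for patients: "divided by the number of evaluable patients who had sufficient follow up (e.g., at least discharge visit"). The term *milestone visit* occurs only in these two sections and is defined in neither.
- **Out-of-window example.** SAP 11 refers to "subjects who are known to be free of events past discharge but missed the discharge visit"; protocol 16.11 refers to "patients who are known to be free of events past discharge eligibility but missed the discharge visit". Both are tied to discharge, not to Day 30.
- **Imputation.** SAP 11: "For all primary and secondary analyses, no imputation of missing data is planned". Protocol 16.11 adds that "the denominator will be adjusted for missing follow up data".
- **Loss to follow-up.** Protocol 14.5 includes "Failure to reach/hear from the subject for the final protocol-required follow-up visit after all required contact attempts have been made".
- **Unit.** Protocol 16.9.1: "The safety analysis will be completed on a per-limb basis". SAP 8.4.1 and the safety sensitivity analysis in SAP 11 also count limbs.

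**The concern.** The follow-up example does not fit the endpoint. If a discharge visit is enough, an event-free subject who disappears the next day is counted as free of major complications through Day 30. That is single imputation of a favourable outcome, in a paragraph that says nothing is imputed. It also cannot establish the 30-day nerve-injury component.

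Two consequences follow. First, two programmers could build different safety denominators from the same paragraph, and trial success requires the safety endpoint (protocol 16.9.1). Second, the SAP 11 tipping-point analysis varies unobserved outcomes. If the same rule decides which limbs enter the GEE and which outcomes count as observed, subjects lost after discharge never become unobserved, and the analysis meant to test them passes them by.

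**Working it through.** **1. The plan's own figure.** Inputs from SAP 5: 1.5% in both groups, 5-point margin, one-sided 0.025. Groups of 136 and 68 are from the protocol synopsis.

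SE = sqrt(0.015×0.985/136 + 0.015×0.985/68) = 0.01805. Power = Φ(0.05/0.01805 − 1.96) = Φ(0.81) = 79.1%. The stated value is about 80%, so it reproduces.

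**2. Assumptions.** The documents give no safety loss rate and call missing safety data unlikely. The 5% they state is for time to ambulation and time to hemostasis. They give no timing of events. So L (loss after discharge) and f (share of events after discharge) are assumed: L from 1% to 10%, f from 0.5 to 1, one limb per subject. The rule is assumed to govern the primary test.

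**3. Error at the margin under the discharge rule.** True rates 6.5% (device) and 1.5% (control), so the true difference is 5 points. Each observed rate is p(1 − fL), with all 136 and 68 retained. Error = Φ((0.05 − diff)/SE − 1.96), with SE at the observed rates.

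Example, L = 5% in both arms, f = 0.5: rates are 0.06338 and 0.01462, difference 0.04875, SE 0.02546. Error = Φ(0.00125/0.02546 − 1.96) = Φ(−1.91) = 2.80%.

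| Equal loss | Normal, f = 0.5 / 1 | Exact enumeration of the same Wald rule, f = 0.5 / 1 |
|---|---|---|
| 0% | 2.50% | 3.16% |
| 1% | 2.56 / 2.62% | 3.25 / 3.34% |
| 2% | 2.62 / 2.74% | 3.34 / 3.53% |
| 5% | 2.80 / 3.14% | 3.62 / 4.15% |
| 10% | 3.14 / 3.95% | 4.15 / 5.41% |

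At 5% loss with f = 0.5 the rule adds 0.30 points (normal) or 0.46 (exact). The Wald approximation alone adds 0.66 with no loss.

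**4. Direction.** At the margin, the observed difference shrinks by f(0.065·L_device − 0.015·L_control). This turns negative when control loss exceeds 0.065/0.015 = 4.33 times device loss. With 10% loss in control only, error is 2.2-2.3% (normal). With equal true rates and equal loss, both rates shrink alike and the difference is unbiased.

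**5. After a 30-day rule.** Evaluable share = (1 − L) + L·p(1 − f); rate = p(1 − fL)/share. Power at 1.5% in both arms, f = 0.5 / 1: 77.9 / 78.3% at 2% loss, 76.0 / 77.0% at 5%, 72.6 / 74.8% at 10%. With f = 0.5 a true 1.5% appears as 1.54% at 5% loss and 1.58% at 10%, because early events in lost subjects are kept. Error at the margin is then 2.25% and 2.0% (normal); with f = 1 it is 2.5%.

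**The case against.** The discharge visit is introduced as an example and with a minimum qualifier, so it is not a stated rule. The surrounding text leans towards 30 days: the endpoint definition, the ban on imputation, protocol 14.5 on loss to follow-up, the adjusted denominator in protocol 16.11, and SAP 8.1, which assumes 30-day follow-up is complete when the analysis is run. The formula is a subject-level rate, while the test is a per-limb GEE risk difference, and neither document says the first feeds the second. Unobserved, in its ordinary sense, would include a limb with unknown 30-day status. Missing safety data are called unlikely, and protocol 14.4 allows the visit by phone.

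Most of this stands. A reader might infer that the plan fixes discharge as the evaluability criterion, or that Type I error for safety is inflated. The documents support neither: the first overlooks that discharge is only an example, and the second needs a link to the GEE and a loss rate that are not stated. What the objection does not supply is a rule. The lines that lean towards 30 days do not say when a limb without a 30-day visit is evaluable, and the only illustrations given point to discharge. If the formula does not govern the GEE, the plan names the ITT population and the 30-day outcome but no follow-up criterion for entry.

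**Conclusion.** The point holds as an inconsistency in the text that should be corrected. The example of sufficient follow-up does not match the 30-day endpoint, the milestone visit is undefined, and the mapping from subjects to limbs is missing.

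The numerical effect is conditional on the rule governing the GEE and on assumed loss and event timing. It is negligible at 1-2% loss and modest at 5%: 2.8-3.1% against 2.5% by normal approximation, or 3.6-4.2% against 3.2% by exact enumeration. The 10% row is an assumption with no support in the documents. A reader might also infer a systematic bias towards the device. That does not follow: under the plan's assumption of equal rates, equal loss leaves the difference unbiased, and at the margin the direction depends on which arm loses more. The reason to act is that the primary safety denominator should be unambiguous before the data are seen.

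**What to change.** Put one rule in both documents:

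*For the 30-day major-complication rate the milestone visit is the 30 ± 7-day visit, counted from the index procedure. A limb is evaluable if it has a CEC-adjudicated major complication through Day 30 post procedure, or if its event-free status is ascertained at that visit (on site or by phone) or later. This rule defines the limbs in the primary GEE analysis. All other limbs, including those of subjects who die or withdraw event-free before that visit, are unobserved and enter the SAP 11 tipping-point analysis.*

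Replace both discharge-based examples with wording on the same standard, such as *subjects who missed the 30-day visit but whose event-free status was ascertained later*. Reconcile protocol 14.7, which counts the final visit from discharge, with the endpoint, which counts from the procedure.

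**Cost.** One paragraph in each document and no new data collection. Nominal safety power falls as in step 5, to 76-77% at 5% loss. The rule has a small bias of its own, since early events in lost subjects are kept while event-free lost subjects are dropped. Accepting a visit from Day 23 leaves up to a week unobserved for some subjects; a later cut-off would lose more of them.

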5 SAMPLE SIZE

All sample sizes were calculated assuming a 2:1 ratio of MYNX CONTROL[™] VCD to manual compression.

Time to Ambulation:

Time to ambulation is a co-primary endpoint for effectiveness. The Type 1 error for this calculation was set at 0.025 for a one-sided test. Assuming that the treatment group ambulates in 3.0 hours on average and the control group ambulates in 6.0 hours and both groups have a standard deviation of 6.0 hours, then an effective sample size of 192 subjects provides 90% power to detect this difference in time to ambulation between the two groups of subjects. Adjusting for a missing data rate of 5%, total enrollment is 204 subjects.

Time to Hemostasis:

Time to hemostasis is a co-primary endpoint for effectiveness. The Type 1 error for this calculation was set at 0.025 for a one-sided test. A generalized linear mixed model will be used to compare the MYNX CONTROL[™] Venous VCD device with manual

compression (control). Initial estimates of the average time to hemostasis were taken from historical MYNX family devices and compared to manual compression. Previous MYNX family studies only studied one access site per subject within the femoral artery. The observed average time to hemostasis as well as the standard deviations of those measurements helped inform the design of this trial where the standard deviation would be used as an estimate of subject-to-subject variation. For the sample size calculation, it is assumed that each subject has 3 access sites in the femoral vein. These access sites will be closed with either the MYNX CONTROL[™] Venous VCD device or manual compression. Only one method of closure will be used per subject. Time to hemostasis will be measured for each access site separately.

It is assumed that hemostasis times are log-normally distributed. Using previous study data where time to hemostasis averaged 6 minutes for the MYNX CONTROLTM Venous VCD device and 13 minutes for manual compression, estimates of μ and σ of the lognormal distribution were obtained and used in the calculation of sample size for this endpoint.

A generalized linear mixed model is used with the subject as a random effect. The specific model used is:

$$y_{ijk} = \mu + \tau_i + S_{j(i)} + e_{k(ij)}$$

where τ_i is the treatment effect and S_{ij} is the random effect of subject within treatment. e_{ijk} is the unexplained variation in the model. Further, it is assumed that:

$$y_{ijk} \sim N(\mu_{ij}, \sigma^2)$$

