8.5 Analyses of Effectiveness Endpoints

8.5.1 Primary Effectiveness Endpoint Analysis

There are two co-primary effectiveness endpoints: Time to hemostasis, and time to ambulation.

The average time to ambulation in each treatment group will be compared using a standard T-test. The test will be done on a per subject basis. The null and alternative hypotheses are:

Ho: $\mu_{Mynx \ Control} \geq \mu_{manual \ compression}$

Ha: $\mu_{Mynx \ Control} < \mu_{manual \ compression}$

where μ_x is the average time to ambulation for the specified group. A p-value for this one-sided test less than 0.025 will indicate that the time to ambulation for the subjects using the MYNX CONTROLTM Venous VCD was significantly less than for those where manual compression was used.

The average time to hemostasis will be analyzed on an access site level. The null and alternative hypotheses of the primary effectiveness comparison for TTH are given below:

Ho: $\mu_{manual \ compression} - \mu_{Mynx \ Control} \le 5$ Ha: $\mu_{manual \ compression} - \mu_{Mynx \ Control} > 5$

where μ_x is the mean time to hemostasis for the indicated group and 5 minutes is superiority margin.

The average time to hemostasis will be analyzed using a generalized linear mixed model where subject is considered a random effect with multiple access sites and treatment group is a fixed effect. The times to hemostasis in the manual compression group will be reduced by 5 minutes to account for the hypothesis that the time to hemostasis for the MYNX CONTROL[™] Venous VCD device is at least 5 minutes less than manual compression. The analysis will consist of testing the coefficient on the fixed effect for treatment group. If that coefficient is found to be significantly different from zero, then the direction will be evaluated to assure that the hemostasis time is reduced on average when using MYNX CONTROL[™] Venous VCD. This test is by default a two-sided test, so a p-value of 0.05 or less with the direction of the difference showing shorter times for MYNX

CONTROL[™] Venous VCD will correspond to a one-sided test at the 0.025 level results in achieving this endpoint.

If the distribution assumptions (normality, lognormality) for the primary effectiveness endpoints do not hold based on Shapiro-Wilk test at the 0.05 alpha level, a non-parametric Wilcoxon rank sum test will be used to compare the treatment groups.

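### The missing-data tipping-point analysis is defined only on arm means, yet the SAP switches the deciding test to Wilcoxon when normality fails, which is the expected case for time to ambulation

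*SAP*

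**What the plan says.** SAP section 11 plans no imputation for the primary and secondary analyses. It then describes a simple pattern mixture sensitivity analysis for TTH, TTA and TTDE: "For each treatment group, the overall mean is a weighted average of the observed data and the unobserved data". In the control arm the unobserved mean equals the observed mean. In the device arm the unobserved mean is raised step by step (1 minute for TTH, 0.5 hour for TTA and TTDE) until the endpoint's interpretation changes. The section names no test, standard error or scale, and has no version for a rank test. Protocol section 16.11 leaves the details to the SAP.

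SAP section 8.5.1 compares TTA by t-test and TTH by a mixed model. If the normality or lognormality assumption fails Shapiro-Wilk at 0.05, "a non-parametric Wilcoxon rank sum test will be used to compare the treatment groups". Section 8.5.2 sets the same rule for TTDE, with normality as the assumption. Protocol section 16.9.1 names only the t-test for TTA.

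For TTA, SAP section 5 assumes that "the treatment group ambulates in 3.0 hours on average and the control group ambulates in 6.0 hours" and that "both groups have a standard deviation of 6.0 hours".

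**The concern.** A tipping-point analysis should show how adverse the missing data must be before the declared conclusion fails. It therefore has to act on the test that produced the conclusion. Moving an arm mean by a weighted Δ changes a t-statistic, but it does not say where the missing patients rank, so a Wilcoxon p-value cannot be recomputed from it. If the fallback is used, section 11 as written yields a Δ for a different test.

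TTA is a co-primary endpoint, and Protocol section 16.9.1 requires both efficacy endpoints and the safety endpoint for trial success. The section 11 analysis is the only missing-data check stated for TTA, TTH and TTDE. A Δ from the wrong test could make the TTA result look more fragile than it is, or appear to contradict it.

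**Working it through.** **1. Reproduce the plan's TTA figure.** Inputs from SAP section 5: difference 6 − 3 = 3 h; SD 6 h; "The Type 1 error for this calculation was set at 0.025 for a one-sided test"; "All sample sizes were calculated assuming a 2:1 ratio"; "an effective sample size of 192 subjects provides 90% power to detect this difference in time to ambulation".

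- With 128 and 64 patients, SE = 6 × √(1/128 + 1/64) = 0.919 h, and 3 / 0.919 = 3.27. Noncentral-t power is 90.1%, so 192 reproduces.
- "Adjusting for a missing data rate of 5%, total enrollment is 204 subjects": 192 / 0.95 = 202.1, so 203, or 204 at 2:1.
- At 5% missing, 136 × 0.05 = 6.8 and 68 × 0.05 = 3.4. I take 7 and 3 missing, leaving 129 and 65 observed.

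**2. Are those figures compatible with normal TTA?** An elapsed time cannot be negative. Under normality, P(device < 0) = Φ(−3/6) = 30.9% and P(control < 0) = Φ(−6/6) = 15.9%. The planning values therefore imply strong right skew.

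**3. How often would the switch occur?** Simulated trials used means of 3 and 6 h with 129/65 observed. The lognormal and gamma shapes, and every SD other than 6 h, are assumptions. The 1.3/1.9 h pair is borrowed from the TTDE figures in SAP section 5.

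| SD device/control | Shapiro-Wilk rejects (raw-scale residuals) | Wilcoxon significant, t-test not |
|---|---|---|
| 6 / 6 h | 100% | about 10-12% (single runs up to 13%) |
| 4 / 4 h | 100% | about 1% (0.4% gamma, 1.5% lognormal) |
| 3 / 3 h | 100% | 0-0.1% |
| 1.3 / 1.9 h | 93% (gamma) to over 99% (lognormal) | 0% |

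The switch becomes less likely in three cases:
- At very tight SDs (0.6/1.2 h), residuals reject in 80-91%.
- If TTA is truly normal within arms, at least one arm rejects in only 8-11%.
- If Shapiro-Wilk may be applied on the log scale and the data are truly lognormal at SD 6 h, it rejects in about 11-12%.

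**4. Mean-based tipping point at the planning values.** The device mean rises by (7/136)Δ = 0.0515Δ.

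- SE = 6 × √(1/129 + 1/65) = 0.913 h, and 1.96 × 0.913 = 1.789 h.
- Δ = (3 − 1.789) / 0.0515 = 23.5 h.
- Suppose the shifted group also adds spread, with π = 7/136. Then 3 − πΔ = 1.96 × √(0.913² + π(1 − π)Δ²/136), which gives Δ of about 20.5 h.

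In simulation at SD 6 h, among trials where the t-test was significant, the median was about 26-31 h, or about 22-25 h with the added spread. These exceed the analytic values because they are conditional on a significant t-test.

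**5. The same question for the rank test.** At SD 6 h and 5% missing, Wilcoxon was significant in 100% of trials. It stayed significant in 100% with all 7 missing device patients ranked last, so no tipping point exists. At an assumed 15% missing, it still held in 98-99%, while the mean-based median tip fell to about 9-11 h.

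**The case against.** **The mismatch starts in section 8.5.1, not section 11.** The TTA, TTH and TTDE hypotheses concern means, and the protocol names a t-test for TTA, so a mean shift matches the stated target. This is fair: dropping the Wilcoxon fallback would also remove the TTA mismatch. But the SAP as written contains both rules, and section 11 has no branch for the second.

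**The switch is not certain.** This stands. The rule is conditional. The SAP does not say whether Shapiro-Wilk is applied per arm, to residuals or to pooled data, and its reference to lognormality is not tied to one endpoint. Section 5 states lognormality only for TTH, so a log-scale check for TTA is an arguable reading rather than a stated one. A reader might infer that TTA will definitely be decided by Wilcoxon; the documents support only that this is expected.

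**The disagreement at Δ = 0 is not a missing-data effect.** This also stands. A reader might infer that missing data would overturn about one result in nine. The 10-12% is essentially the type II error of a t-test designed for 90% power, counted where Wilcoxon succeeds. It would occur with complete data, and it vanishes at tighter SDs.

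**Section 11 is silent on programming detail.** A reader might infer that it drops the TTH subject effect, or ignores the spread added by the shifted patients. The text does not say so; it gives no variance formula or model. Likewise, its ban on imputation covers the primary and secondary analyses, not this sensitivity analysis. The supportable claim is that the only quantity it defines is an arm mean.

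**Conclusion.** The point holds as a mismatch between the sensitivity analysis and the test expected to decide TTA. The same gap applies to TTH and TTDE whenever their fallback is triggered, although the likelihood of that was not quantified here.

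The numerical tipping points assume lognormal or gamma TTA at the plan's means, an SD of 6 h and 5% missing. On those assumptions the SAP's method would report about 26-31 h (22-25 h with added spread) for a conclusion that, under the deciding test, does not tip at all.

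A reader might go further and infer that the primary TTA result would be wrong or fragile. The calculations show the opposite: the rank conclusion is robust at the planned missing rate. Trial success also does not depend on this analysis. The practical effect is modest, but the change should be made because the robustness statement would otherwise describe the wrong test.

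**What to change.** In SAP section 11, replace the weighted-mean step for TTA, TTH and TTDE with the following:

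1. Impute individual missing values in each arm from that arm's observed distribution.
2. Add Δ to the imputed device-arm values only, keeping the present increments.
3. Re-run whichever test decided the endpoint. For TTH, keep the 5-minute reduction, and keep the subject effect when the mixed model decides.
4. Report the Δ at which that test loses significance, or state that none exists.

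This works whichever test sections 8.5.1 and 8.5.2 select. It costs SAP wording and a small amount of programming, with no new data and no additional patients. The downside is that repeated imputations must be combined, so the SAP should state the number of imputations and the combining rule, including for the Wilcoxon case.
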